**Table 16-4 Renal event follow-up**

---

**FOLLOW-UP OF RENAL EVENTS**

---

Assess, document and record in CRF

- Urine dipstick and sediment microscopy evidence of Drug-Induced Nephrotoxicity (DIN): crystals, red blood cells (dysmorphic/glomerular vs. non-dysmorphic/non-glomerular), white blood cells, tubular epithelial cells
- Blood pressure and body weight
- Serum creatinine, BUN, electrolytes (sodium, potassium, phosphate, calcium), bicarbonate and uric acid
- Urine output

---

Review and record possible contributing factors to the renal event (co-medications, other co-morbid conditions) and additional diagnostic procedures (MRI etc.) in the CRF

---

Monitor patient regularly (frequency at investigator's discretion) until

- Event resolution: (sCr within 10% of baseline or PCR < 1 g/g Cr, or ACR <300 mg/g Cr) or
- Event stabilization: sCr level with  $\pm 10\%$  variability over last 6 months or protein-creatinine ratio stabilization at a new level with  $\pm 50\%$  variability over last 6 months.
- Analysis of urine markers in samples collected over the course of the DIN event

## 16.4 Appendix 4: Prohibited medications

The lists provided in the table below are non-exhaustive. In case of any doubt, the corresponding SmPC should be checked.

**Table 16-5 Moderate and strong inhibitors of CYP3A4**

Strong inhibitors of CYP3A4	boceprevir, clarithromycin, cobicistat, conivaptan, danoprevir/ritonavir, darunavir/ritonavir, elvitegravir/ritonavir, grapefruit juice, idelalisib, indinavir, indinavir/ritonavir, itraconazole, ketoconazole, LCL161, lopinavir/ritonavir, mibepradil, nefazodone, neflifinavir, posaconazole, ritonavir, saquinavir, saquinavir/ritonavir, telaprevir, telithromycin, tipranavir/ritonavir, troleandomycin, Viekira pack, voriconazole
Moderate inhibitors of CYP3A4	ACT-178882, amprenavir, aprepitant, atazanavir, casopitant, cimetidine, ciprofloxacin, crizotinib, cyclosporine, darunavir, diltiazem, dronedarone, erythromycin, faldaprevir, ferula asafetida resin (herbal product), FK1706, fluconazole, imatinib, isavuconazole, netupitant, nilotinib, schisandra, sphenanthera, tofisopam, verapamil

**Table 16-6 Moderate and strong inducers of CYP3A4**

Strong inducers of CYP3A4	avasimibe, carbamazepine, enzalutamide, ifampin, mitotane, phenobarbital, phenytoin, rifabutin, St. John's wort (herbal product)
Moderate inducers of CYP3A4	bosentan, efavirenz, etravirine, iesivirine, lopinavir, modafinil, nafcillin, ritonavir/tipranavir, semagacestat, talviraline, thioridazine

**Document History – Changes compared to previous final version of SAP**

Date	Time point	Reason for update	Outcome for update	Section and title impacted (Current)
9- Sep- 2019	Prior to FPFV	Creation of final version	First version	NA
Jun- 2021	[REDACTED]	Protocol amendment v2.0  Address comment from dry-run review  Update the analysis visit window for eDiary assessment		Section 2.1.1.3 Update the assessment window for eDiary assessment (i.e. UAS7, [REDACTED]);  Section 2.3.2 Add baseline characteristics;  Section 2.5.1.1 Update the treatment emergent adverse event definition; Drop Table 2-2;  Section 2.5.1.2 Update the CTCAE grade definition in Table 2-3  Section 2.5.1.3 Update the notable abnormality criterion in ECG;  Section 2.5.1.4. Update the notable abnormality criterion in vital signs;  Section 2.6.3 Drop the handling rule for duplicated UPDD entries;  Section 2.13 text updated for more clarity on population included for IA2
Oct- 22	Prior to final analysis	Update for protocol deviation		Additional details added to Section 2.3.1 for protocol deviation analysis

Date	Time point	Reason for update	Outcome for update	Section and title impacted (Current)
		Updates for demog and baseline characteristic		More details are added to clarify that sex, race and ethnicity collected from core study.
		Medical History		Urticaria related medical history summaries added
				Medical history and current medical condition listings are added
		Study treatment/compliance		More details are added for calculations of exposure (weeks), exposure (years) and exposure (100 subject years)
		Section 2.4.2		Concomitant surgeries, medical procedures and non-drug therapies added
				Listing for Prior and concomitant medication included

## List of abbreviations

AE	Adverse Event
ALP	Alkaline Phosphatase
ALT	Alanine Aminotransferase
AST	Aspartate Aminotransferase
ATC	Anatomical Therapeutic Classification
b.i.d.	bis in diem/twice a day
BP	Blood Pressure
CSR	Clinical Study report
CSU	Chronic Spontaneous Urticaria
CV	Coefficient of Variation
CTCAE	Common Terminology Criteria for Adverse Events
ECG	Electrocardiogram
EOT	End of treatment period
EOS	End of study period
FAS	Full Analysis Set
GCP	Good Clinical Practice
HSS7	Weekly Hives Severity Score
Ig	Immunoglobulin
INR	International Normalized Ratio
IRT	Interactive Response Technology
ISS7	Weekly Itch Severity Score
LLN	Lower Limit of Normal
LLOQ	Lower Limit of Quantification
MedDRA	Medical Dictionary for Drug Regulatory Affairs
QTcF	QT interval corrected by Fridericia's formula
SAE	Serious Adverse Event
SAF	Safety Analysis set
SAP	Statistical Analysis Plan
SD	Standard Deviation
SMQ	Standardized MedDRA Query
SOC	System Organ Class
TBL	Total bilirubin
ULN	Upper Limit of Normal
ULOQ	Upper Limit Of Quantification
UPDD	Urticaria Patient Daily Diary

## 1 Introduction

Data will be analyzed by Novartis according to the data analysis section 12 of the study protocol which is available in [Appendix 16.1.1 of the CSR](#). Important information is given in the following sections and details are provided, as applicable, in [Appendix 16.1.9 of the CSR](#).

This document covers statistical and analytical plans [REDACTED] for the final analysis of all data collected up to end of the study for CLOU064A2201E1 study with reference to the study protocol.

[REDACTED]

### 1.1 Study design

This study is an open-label, single arm, multicenter, long-term safety and tolerability extension study for CSU patients who have participated in CLOU064A2201 or other preceding studies with LOU064 and fulfil the enrollment criteria for the extension study.

The study will consist of three periods: observational period (up to 12 weeks), treatment period (52 weeks), and follow-up period (4-16 weeks).

Approximately 250 patients will enroll into this extension study.

The following study periods will be considered for analysis:

- **Observational period** (Enrollment in observation period to end of observation period (up to Week 12))
- **Treatment period** (Enrollment in treatment period to Week 52 including follow-up visits for patients prematurely discontinued)
- **Entire study period** (Enrollment in treatment period to EoS (End of study) including follow-up visits for all patients)

### 1.2 Study objectives and endpoints

[figure not shown]
The purpose of this study is to evaluate long-term safety and tolerability as well as efficacy outcome of LOU064 in patients who have participated in a preceding study with LOU064 in CSU.

[REDACTED]

**Table 1-1 Objectives and related endpoints**

Objective(s)	Endpoint(s)

Primary Objective(s)	Endpoint(s) for primary objective(s)

• To assess the long-term safety and tolerability of LOU064 in patients with CSU who have participated in preceding studies with LOU064.

	

• Safety endpoints will include but not be limited to: occurrence of treatment emergent (serious and non-serious) adverse events during the extension study

Secondary Objective(s)	Endpoint(s) for secondary objective(s)

• To evaluate the efficacy of LOU064 when given without H1-antihistamines in patients with CSU with respect to change from baseline in UAS7, achieving controlled disease (defined by a UAS7≤6), and achieving complete response (defined by a UAS7=0) at Week 4 of treatment

	

• Change from baseline in UAS7 at Week 4

• UAS7≤6 response at Week 4

• UAS7=0 response at Week 4

• To evaluate the long-term efficacy of LOU064 in patients with CSU who have participated in previous studies with LOU064 with respect to maintaining or achieving controlled disease (defined by a UAS7≤6) over time

	

• UAS7≤6 response over time

• To evaluate the long-term efficacy of LOU064 in patients with CSU who have participated in preceding studies with LOU064 with respect to change from baseline in UAS7 over time

	

• Change from baseline in UAS7 over time

## **2 Statistical methods**

Novartis will be performing [REDACTED] the final analysis. Statistical software R version 3.4.3 and SAS version 9.4 or later will be used.

### **2.1 Data analysis general information**

Summary statistics for continuous variables will include N, mean, standard deviation, minimum, lower quartile, median, upper quartile, maximum.

Summary statistics for discrete variables will be presented in contingency tables and will include absolute and relative frequencies.

#### **2.1.1 General definitions**

##### **2.1.1.1 Study treatment**

The following treatment groups will be presented:

- LOU064 100 mg b.i.d.
- Treatment free

##### **2.1.1.2 Study Day 1 and Study Day for treatment period**

For safety analysis, the day of first dose of study treatment is defined as *Study Day 1* or *Day 1*.

For efficacy analysis, the day of enrollment in treatment period (visit 101) is defined as *Study Day 1 or Day 1*.

Study days will be labeled relative to Day 1 for treatment period. For event dates on or after Day 1, study day for a particular event date is calculated as [Date of event] – [Date of first dose/Enrollment] + 1, i.e., Day 2, Day 3, etc., will be one day, two days, etc., after Day 1, respectively.

For the dates before Day 1, study day for an event date is calculated as [Date of event] – [Date of first dose/Enrollment], i.e., Day -1, Day -2, etc., will be one day, two days, etc., before Day 1, respectively. Duration of an event will be calculated as (Event end date – Event start date + 1). The descriptor “Day 0” will not be used.

### 2.1.1.3 Assessment window for Study Week (eDiary)

The study weeks for assessment completed on eDiary are defined based on the study days starting with Day 1 (Enrollment in observational/treatment period Day).

For completers of treatment period, the study day for eDiary date will be calculated as [Date of Diary] – [Date of Enrollment] + 1 for post-baseline assessment and [Date of Diary] – [Date of Enrollment] for baseline assessment. The analysis Week 1 through Week 51 of the treatment period will be derived based on scheduled visit day as defined in [Table 2-1](#). The analysis Week 52 score will be derived as Day -7 to Day -1 of actual Week 52 study visit day.

During the follow-up period, the study weeks for assessment completed on eDiary are defined based on the study days starting with Day 1 of follow-up period (actual Week 52 visit day). The study day for the eDiary date will be calculated as [Date of Diary] – [Date of Week 52 visit day] + 1. The analysis follow-up Week 1 to Week 16 will be derived based on the actual Week 52 study visit day as defined in [Table 2-1](#).

For early discontinued patients, it is suggested to collect the eDiary data even after the patient discontinued from treatment per “Treatment policy strategy” (this part of data is named as “retrieved drop-out data”). The retrieved drop-out data will be included in the weekly score derivation per assessment window defined in [Table 2-1](#).

**Table 2-1      Assessment window for eDiary**

Period	Analysis visit	Scheduled Visit Day	eDiary Assessment Window
Observational	OEnrollment	1	Day -7 to Day -1
	OWeek 1	-	Day 1 to Day 7
	OWeek 2	-	Day 8 to Day 14
	OWeek 3	-	Day 15 to Day 21
	OWeek 4	29	Day 22 to Day 28

	OWeek 5	-	Day 29 to Day 35
	OWeek 6	-	Day 36 to Day 42
	OWeek 7	-	Day 43 to Day 49
	OWeek 8	57	Day 50 to Day 56
	OWeek 9	-	Day 57 to Day 63
	OWeek 10	-	Day 64 to Day 70
	OWeek 11	-	Day 71 to Day 77
	OWeek 12	85	Day 78 to Day 84
Treatment	Baseline	1	Day -7 to Day -1
	Similar as in observational period.		
	Week 12	85	Day 78 to Day 84
	...		
	Week 16	113	Day 106 to Day 112
	...		
	Week 20	141	Day 134 to Day 140
	...		
	Week 28	197	Day 190 to Day 196
	...		
	Week 40	281	Day 274 to Day 280
	...		
	Week 52	365	Day 358 to Day 364 For completers, Day -7 to Day -1 of Week 52 study visit
Follow-up	Follow-up Week 1	393	Day 1 to Day 7 of Week 52 study visit
	...		
	Follow-up Week 4	421	Day 22 to Day 28 of Week 52 study visit
	...		
	Follow-up Week 12	477	Day 78 to Day 84 of Week 52 study visit

The baseline week is comprised of the 7 days prior to Day 1 (Day -7 to Day -1). The baseline UAS7 score for observational period could be different from the UAS7 score of the last visit for core study. The baseline UAS7 score for treatment period could be different from the UAS7 score of the last visit for observational period.

#### **2.1.1.4 Baseline**

Baseline for safety in treatment period is the last assessment (including unscheduled visits) obtained on or before the first dose day of study treatment. All assessments obtained after the first dose of study treatment are considered as post-baseline unless otherwise specified.

Baseline for efficacy in treatment period is comprised of the 7 days prior to Day 1 (Enrollment in treatment period Day) for UAS7 and other assessment on or prior enrollment in treatment period day.

For observational period, only baseline UAS7 score is applicable and defined in [section 2.1.1.3](#).

#### **2.1.1.5 On-treatment**

All safety events happened after first dose of study treatment and before minimum(last dose + 28days, end of study visit) will be considered on-treatment no matter during treatment period or follow-up period.

For AE summary for observational period, all adverse event happened after enrollment in observational period and before roll over to treatment period will be summarized.

### **2.2 Analysis sets**

The following analysis sets will be used for the data analysis, details refer to [section 5.5](#).

The **Safety Analysis Set** includes all subjects who received at least one dose of study treatment during the treatment period of this extension study.

For the observational period, the observational **Full Analysis Set (oFAS)** includes all subjects who enrolled in the observational period.

All enrolled subjects includes all subjects who enrolled in this extension study.

### **2.3 Patient disposition, demographics and other baseline characteristics**

#### **2.3.1 Patient disposition**

The number of screened and screen failures subjects will also be shown for all enrolled subjects. The reason for screen failure will be summarized.

The number of subjects in each analysis set will be presented by observational period based on oFAS and treatment period based on Safety set. The reason for excluded from any analysis set will be listed.

The number and percentage of patients enrolled in observational period, complete observation period or early discontinued from study during observational period will be presented based on oFAS. Similarly, the number and percentage of patients enrolled in treatment period, complete the treatment period or early discontinued from treatment/study will be presented based on SAF.

The number and percentage of patients who has experienced protocol deviations (PD) will be tabulated by deviation category for all patients.

Listing will be provided for all subjects enrolled.

### 2.3.2 Demographic and baseline characteristics

Demographics and baseline characteristics will be summarized for treatment period based on SAF and for observational period based on oFAS. Disease characteristics and relevant medical histories will also be presented based on SAF. Subject demographic and baseline characteristic data including sex, race and ethnicity that was collected as a part of the core study will be used in this extension study.

Listing will be provided for all subjects enrolled.

Summary statistics will be presented for continuous demographic and baseline characteristic variables for all patients.

## Continuous variables:

- Age (years) (for A2201E1 study)
- Height (cm)
- Weight (kg)
- Body mass index (BMI) = (body weight in kilograms) / (height in meters)
- Baseline UAS7 score/Enrollment UAS7 score
- [REDACTED]
- [REDACTED]
- Time since diagnosis of urticaria = (inform consent date – diagnosis date + 1)/365.25

The number and percentage of subjects in each category will be presented for categorical variables for all patients.

## Categorical variables:

- Age categories (< 65,  $\geq 65$ -<85 years,  $\geq 85$  years)
- Gender (from core study A2201)

- Race (from core study A2201)
- Ethnicity (from core study A2201)
- BMI groups (< 25, 25 - 30, >= 30 kg/m\*\*2)
- Baseline UAS7 category (Mild disease: UAS7 6-<16; Moderate disease: UAS7 16-<28; Severe disease UAS7 28-42)/Enrollment UAS7 category

■ [REDACTED]

### **2.3.3 Medical history**

Relevant medical histories and current medical conditions before first dose of study treatment in the treatment period will be summarized by system organ class and preferred term according to MedDRA dictionary for SAF. Urticaria related medical history will be summarized separately for SAF.

All relevant medical histories and current medical conditions will be listed for all subjects enrolled. Cardiovascular history and family malignancy history for subjects developed malignancy during the treatment period will be listed for SAF

## **2.4 Treatments (study treatment, rescue medication, concomitant therapies, compliance)**

The analysis of study treatment data will be based on SAF.

### **2.4.1 Study treatment / compliance**

The duration of exposure to study treatment and duration of study will be summarized for SAF. In addition, the number of subjects with exposure of at least certain thresholds (eg, any exposure,  $\geq 1$  week,  $\geq 2$  weeks,  $\geq 4$  weeks,  $\geq 8$  weeks, etc.) will be displayed.

**Duration of exposure** is defined as last dose of study treatment – first dose of study treatment + 1.

[figure not shown]
**Duration of study for entire study period** is defined as last study visit – enrollment in treatment period + 1.

Duration of exposure (weeks) = duration of exposure (days) / 7

Duration of exposure (years) = duration of exposure (days) / 365.25

Duration of exposure (100 subject years) = duration of exposure (years) / 100

The start date and end date of study treatment will be collected on eCRF and will be used to calculate the duration of exposure.

#### **2.4.2 Prior, concomitant and post therapies**

Prior, non-urticaria related concomitant medications and urticaria related concomitant medication or rescue medications during treatment period will be summarized by Anatomical Therapeutic Chemical (ATC) code and preferred term for SAF. Additionally, concomitant surgeries, medical procedures and non-drug therapies by primary system organ class and preferred term will be preseted.

Concomitant medications are defined as any medication given at least once between the day of first dose of study treatment and the date of the last study visit.

Background medications and rescue medications during treatment period will be summarized separately by Anatomical Therapeutic Chemical (ATC) code and preferred term for SAF.

Medications will be identified using the Novartis Drug and Therapy Dictionary (NovDTD) including the Anatomical Therapeutic Chemical (ATC) code. Medications will be presented in alphabetical order, by ATC code.

All relevant listings will be provided based on SAF for concomitant medication; concomitant surgeries, medical procedures and non-drug therapies.

## **2.5 Analysis of the primary objective**

The primary objective of this study is to investigate the long-term safety and tolerability of LOU064 in subjects with CSU. The primary safety analysis will be analyzed using SAF.

### **2.5.1 Primary endpoint**

#### **2.5.1.1 Adverse events**

All adverse events which newly start on the same day or after the first dose of study medication in the treatment period of this extension study OR worsen on the same day or after the first dose of study medication and within min(last dose + 28 days, end of study visit) will be considered as treatment emergent adverse event for this extension study.

Number and percentage of subjects having any treatment emergent adverse events during entire study period of the extension study, by system organ class and preferred term will be provided for:

- All adverse events
- Adverse events by maximum severity
- Drug related adverse events
- Serious Adverse events
- Adverse events leading to treatment discontinuation

[figure not shown]
Adverse events by standardized MedDRA Query (SMQ), System organ class (SOC) and preferred term will be provided. Separate summaries will be provided for deaths, SAEs, and other significant AEs leading to discontinuation.

If a subject reported more than one AE with the same preferred term, the AE with the greatest severity will be presented.

All adverse events will be listed for SAF.

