## 4 Rationale

### 4.1 Rationale for study design

The major aims of this extension study are to obtain information on the long-term safety and efficacy of a dosing regimen of LOU064 with a high level of BTK occupancy and therefore pharmacological activity, LOU064 100 mg bid for 52 weeks. An open-label study design was chosen to minimize complexity and placebo exposure for CSU patients who have participated in the dose-range finding study CLOU064A2201. A follow-up period of (up to) 16 weeks after the treatment period will further assess safety.

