 Detailed description of physical exam in [Table 8-9](#). Complete physical exam: day 1 of the treatment period. Short physical exam: all other visits.

 UPDD: Urticaria Patient Daily Diary; UAS: Urticaria Activity Score;

 Only performed in women of childbearing potential

 Only performed in women of childbearing potential. In addition to tests during study visits, urine pregnancy tests can be performed at home at Week 24, 32, 36, 44, and 48. Sites must contact subjects to obtain test results. Any positive or undetermined test result must be confirmed by a serum pregnancy test done by central lab.

 Only assess if day 1 is more than 1 week after roll-over date from core study (Week 12 or Week 16)

 Only assess if subjects rollover at Week 16 or if subjects rollover at Week 12 and day 1 of treatment period is more than 1 week after Week 12 of core study

 EoTV (End-of-Treatment Visit) is after completion of the treatment period (Week 52 Visit), or directly after early discontinuation of study treatment (see [Section 9.1](#))

 Only for subjects eligible for extended follow-up

 Phone call visits: after Week 56, all eligible subjects in extended follow-up should be contacted every 4 weeks by phone until Study Completion visit which is a site visit

 SCV (Study Completion Visit) is 4-16 weeks after EoTV:

- all subjects should be followed-up for a minimum of 4 weeks after EoTV
- the extended follow-up of eligible subjects (completion of treatment period and a UAS7≤6 at Week 52) should be stopped after relapse of CSU, initiation of a prohibited therapy (see [Section 6.2.2](#)), decision of the subject or the investigator to stop the follow-up, rolling-over into a post-trial access program (if available), or reaching the maximum follow-up time (16 weeks, Week 68 Visit)

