All adverse events must be treated appropriately. Treatment may include one or more of the following:

- Dose not changed
- Dose Reduced/increased
- Drug interrupted/withdrawn

6. its outcome
  - not recovered/not resolved
  - recovered/resolved
  - recovering/resolving
  - recovered/resolved with sequelae
  - fatal
  - unknown

Conditions that were already present at the time of informed consent should be recorded in medical history of the subject.

Adverse events (including lab abnormalities that constitute AEs) should be described using a diagnosis whenever possible, rather than individual underlying signs and symptoms.

Adverse event monitoring should be continued for at least 30 days following the last dose of study treatment.

Once an adverse event is detected, it must be followed until its resolution or until it is judged to be permanent (e.g. continuing at the end of the study), and assessment must be made at each visit (or more frequently, if necessary) of any changes in severity, the suspected relationship to the interventions required to treat it, and the outcome.

Information about adverse drug reactions for the investigational drug can be found in the IB.

Abnormal laboratory values or test results constitute adverse events only if they fulfill at least one of the following criteria:

- they induce clinical signs or symptoms
- they are considered clinically significant
- they require therapy

Clinically significant abnormal laboratory values or test results must be identified through a review of values outside of normal ranges/clinically notable ranges, significant changes from baseline or the previous visit, or values which are considered to be non-typical in subjects with the underlying disease. See [Appendix 1](#), [Appendix 2](#) and [Appendix 3](#) for alert ranges for laboratory and other test abnormalities.

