### **10.1.3 SAE reporting**

To ensure subject safety, every SAE, regardless of causality, occurring after the subject has provided informed consent and until 30 days following the last administration of study treatment must be reported to Novartis safety within 24 hours of learning of its occurrence. Detailed instructions regarding the submission process and requirements are to be found in the investigator folder provided to each site.

No pre-specified study endpoints are considered to be exempted from SAE reporting.

1. Screen Failures (e.g. a subject who is screened but is not treated or randomized): SAEs occurring after the subject has provided informed consent until the time the subject is deemed a Screen Failure must be reported to Novartis within 24-hours of learning of its occurrence.
2. Randomized OR Treated Subjects: SAEs collected between time subject signs ICF until 30 days after the subject has discontinued or stopped study treatment.

All follow-up information for the SAE including information on complications, progression of the initial SAE and recurrent episodes must be reported as follow-up to the original episode within 24 hours of the investigator receiving the follow-up information. An SAE occurring at a different time interval or otherwise considered completely unrelated to a previously reported one must be reported separately as a new event.

If the SAE is not previously documented in the Investigator's Brochure or Package Insert (new occurrence) and is thought to be related to the study treatment, a CMO & PS Department associate may urgently require further information from the investigator for health authority reporting. Novartis may need to issue an Investigator Notification (IN) to inform all investigators involved in any study with the same study treatment that this SAE has been reported.

Suspected Unexpected Serious Adverse Reactions (SUSARs) will be collected and reported to the competent authorities and relevant ethics committees in accordance with EU Guidance 2011/C 172/01 or as per national regulatory requirements in participating countries.

Any SAEs experienced after the 30 day period following the last administration of study treatment should only be reported to Novartis Safety if the investigator suspects a causal relationship to study treatment.

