### Adverse events

All adverse events which newly start on the same day or after the first dose of study medication in the treatment period of this extension study OR get worsening on the same day or after the first dose of study medication and within end of study visit will be considered as treatment emergent adverse event for this extension study.

Number and percentage of subjects having any treatment emergent adverse events during the extension study, by system organ class and preferred term will be provided for:

- All adverse events
- Adverse events by maximum severity
- Drug related adverse events
- Serious Adverse events
- Adverse events leading to treatment discontinuation

Adverse events by standardized MedCRA Query (SMQ) and preferred term will be provided. Separate summaries will be provided for deaths, SAEs, and other significant AEs leading to discontinuation. For the definition of AEs and SAEs please see [Section 10.1.1](#) and [Section 10.1.2](#).

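### The documents give no single window for treatment-emergent adverse events and SAP Section 4 declares no change; separately, SAP Table 5-1 can take dosed subjects out of the Safety Analysis Set

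*SAP*

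**What the plan says.** Protocol Table 2-1 and SAP Table 1-1 make the occurrence of treatment-emergent adverse events (TEAEs) the endpoint for the primary objective. Four places bear on the window.

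- **Protocol 12.4.1, Adverse events:** counts events with onset from the day of first dose, or that "get worsening on the same day or after the first dose of study medication and within end of study visit".
- **SAP 2.5.1.1:** has the same two branches, new onset or worsening, but the closing limit is that events "within min(last dose + 28 days, end of study visit) will be considered as treatment emergent adverse event".
- **SAP 2.1.1.5:** all safety events after the first dose and "before minimum(last dose + 28days, end of study visit) will be considered on-treatment no matter during treatment period or follow-up period".
- **SAP 2.5.1.1 with SAP 1.1:** the TEAE tables are to cover the *entire study period*, which SAP 1.1 runs from enrollment in the treatment period to end of study, follow-up visits included.

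The SAP introduction says that data will be analysed "according to the data analysis section 12 of the study protocol". SAP Section 4, the place for departures from the protocol analysis, reads as not applicable. The SAP document history records in its June 2021 entry that the TEAE definition was updated, without a reason specific to that item.

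On the analysis set, Protocol 12.1 and SAP 2.2 define the Safety Analysis Set (SAF) as everyone with at least one dose in the treatment period. SAP 2.2 refers to SAP 5.5 for details. Table 5-1 there removes from the SAF subjects coded INCLxx (consent missing or not obtained), OTHxx (severe site GCP non-compliance) or TRTxx (no treatment taken).

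**The concern.** Two analysts, one following the protocol and one following the SAP, could produce different counts for the primary endpoint. The affected time is follow-up that the protocol set up partly for safety. Protocol 4.1 says: "A follow-up period of (up to) 16 weeks after the treatment period will further assess safety". Adverse events are still recorded in the eCRF during it. Table 8-1 marks them at Days 393, 421 and 449 and at the completion visit, and its footnote 12 says that "after Week 56, all eligible subjects in extended follow-up should be contacted every 4 weeks by phone until Study Completion visit". If the cap governs, most of a full extended follow-up could fall outside the main tables by system organ class and preferred term (SOC/PT), and the SAP would not have declared the departure.

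The SAF issue is separate. A site-level deviation code could take dosed subjects, and so their events, out of the primary safety tables, although the set is defined by dosing alone.

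**Working it through.** There is no power, alpha or sample-size figure to reproduce, because no hypothesis is tested. The check is a comparison of texts and date arithmetic on the nominal visit days.

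**Step 1: one event under each reading.** Take a Week 52 responder (UAS7 ≤ 6 at Week 52) whose last dose is on Day 365 and who is followed to Day 477. An adverse event starts or worsens on Day 450.

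| Reading | New onset | Worsening |
|---|---|---|
| Protocol 12.4.1 | TEAE | TEAE |
| SAP 2.5.1.1, limit attached to worsening only | TEAE | not a TEAE |
| SAP 2.5.1.1, limit attached to both, as SAP 2.1.1.5 supports | not a TEAE | not a TEAE |

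The tabulation period in SAP 1.1 is still open on Day 450. It could be combined with the cap by counting only capped TEAEs within that longer period, but the SAP does not say so.

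**Step 2: size of the gap on the capped reading.**

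Inputs from Protocol Table 8-1: end-of-treatment visit (EoTV) Day 365, Week 56 visit Day 393, phone contacts Days 421 and 449, completion visit Day 393 to Day 477. The last dose L is assumed to be on Day 365 or Day 364. E is the end-of-study visit.

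Gap = E − min(L + 28, E). Post-dose follow-up = E − L.

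| Subject | L | Cap day | E | Gap (days) | Follow-up (days) | Share outside cap |
|---|---|---|---|---|---|---|
| Completer, 4-week follow-up | 365 | 393 | 393 | 0 | 28 | 0% |
| Completer, 4-week follow-up | 364 | 392 | 393 | 1 | 29 | 1/29 = 3.4% |
| Responder, full 16 weeks | 365 | 393 | 477 | 84 | 112 | 84/112 = 75.0% |
| Responder, full 16 weeks | 364 | 392 | 477 | 85 | 113 | 85/113 = 75.2% |

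- Early discontinuers complete 4 weeks after the EoTV, so E = EoTV + 28 and the gap is EoTV − L, the delay between last dose and that visit.
- Per responder staying the full 16 weeks, the excluded time is 84/365.25 = 0.230 to 85/365.25 = 0.233 subject-years.
- With last dose on Day 365, three of the four scheduled adverse-event contacts after the EoTV (Day 421, Day 449, completion) fall after the cap. Day 393 is the fourth.

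The 84 to 85 days is a maximum. Footnote 13 of Table 8-1 ends extended follow-up earlier on relapse, prohibited therapy, a decision to stop, or roll-over. The documents do not say how many subjects enter it, so no study total is calculated.

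**Step 3: the SAF.** Of the three codes in Table 5-1, only TRTxx depends on whether a dose was taken, and it agrees with the definition. INCLxx and OTHxx can apply to a dosed subject. The effect is zero unless one is so coded. For scale only, if all of the approximately 250 expected subjects were dosed, each removal would be 1/250 = 0.4% of the set.

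**The case against.** The case on the other side is substantial.

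- **Wording.** SAP 2.5.1.1 can be read so that the cap limits only worsening events, and SAP 2.1.1.5 defines *on-treatment*, not *treatment emergent*. This stands as an ambiguity. SAP 2.1.1.5 makes the capped reading the more likely one but does not settle it.
- **The cap is reasonable in itself.** Four weeks is the minimum follow-up for everyone, so 28 days roughly equalises drug-free time at risk. This stands. The defect is the unresolved and undeclared difference, not the choice of 28 days.
- **The change is logged.** This is true of the document history. But Section 4 still declares no change, and the two definitions still differ.
- **Table 5-1 is announced.** SAP 2.2 refers to it, and SAP 2.3.1 lists the reasons for exclusion. The removal would therefore be visible, but listing a reason does not put the events back in the tables.

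Four stronger readings are tempting, and the documents do not support them.

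- A reader might infer that the SAP definitely drops every late event from the TEAE tables. The worsening-only reading and the tabulation period to end of study prevent that conclusion.
- A reader might infer that late events disappear from the report. SAP 2.5.1.1 lists all adverse events for the SAF. It also promises separate summaries of deaths and SAEs, which may cover some late events, and redacted SAP text may contain more.
- A reader might set the 28 days against the protocol's 30 days: "Adverse event monitoring should be continued for at least 30 days following the last dose of study treatment", and SAEs "until 30 days following the last administration of study treatment must be reported". Those are collection and reporting minima, not an analysis window, so a shorter analysis window does not breach them.
- A reader might see a contradiction in the listings, because Protocol 12.5.2 lists adverse events for all enrolled subjects and SAP 2.5.1.1 names the SAF. The SAP adopts protocol section 12 and does not withdraw the wider listing, so this is only an editorial point.

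**Conclusion.** The point holds in limited form. The protocol and SAP do not give one window for the primary endpoint, the SAP is unclear within itself, and Section 4 declares no departure. Under the capped reading the difference is negligible for completers with 4-week follow-up. It reaches about 75% of post-dose time only for Week 52 responders who stay the full 16 weeks. These sizes assume nominal visit days, although Protocol section 8 asks only for visits as near the planned day as possible, and a last dose on Day 364 or 365. What is at stake is the reported safety counts, not any test.

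The mismatch between Table 5-1 and the SAF definition is clear in the text, but its effect depends on whether a dosed subject is ever coded. OTHxx is the plainer conflict, because excluding subjects without consent may have grounds that the SAP does not state. Overall the point lies between minor and should-fix, with medium confidence.

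**What to change.** 1. **Window.** State one window in SAP 2.1.1.5 and 2.5.1.1, with the same limit and wording for new-onset and worsening events, and reconcile it with the *entire study period* in SAP 1.1. Then choose one of two routes:
   - Keep the 28-day cap, declare it with a reason in SAP Section 4, and add one SOC/PT table of adverse events and SAEs with onset after the cap up to end of study.
   - Restore the protocol's end-of-study limit and footnote the unequal drug-free time at risk: up to 112 to 113 days for responders in extended follow-up, against about 28 to 29 for other completers.
2. **SAF.** Remove OTHxx from the SAF row of Table 5-1. If the code is ever used, add a sensitivity table excluding the site. If INCLxx stays, state the exception in the SAF definition and report how many dosed subjects it removes.
3. **Editorial.** Align the scope of the adverse-event listing in SAP 2.5.1.1 with Protocol 12.5.2.

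The cost is SAP wording, plus a Section 4 entry and one extra table if the cap is kept, and a sensitivity table only if a site is coded OTHxx. No new data are needed. The drawback of restoring the protocol limit is that the TEAE percentage would mix unequal follow-up, which the footnote must make plain.
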